**Table 2. CCW Chronic Conditions (8)**

Acquired Hypothyroidism	Chronic Kidney Disease
Acute Myocardial Infarction	Chronic Obstructive Pulmonary Disease
Alzheimer's Disease, Related Disorders, or Senile Dementia	Depression
Anemia	Diabetes
Asthma	Glaucoma
Atrial Fibrillation	Hip / Pelvic Fracture
Benign Prostatic Hyperplasia	Hyperlipidemia
Cancer (any of the following): Cancer, Colorectal Cancer, Endometrial Cancer, Breast Cancer, Lung Cancer, Prostate	Hypertension
	Ischemic Heart Disease
	Osteoporosis
	Rheumatoid Arthritis / Osteoarthritis
	Stroke / Transient Ischemic Attack
Cataract	

## STATISTICAL ANALYSIS

### **Estimation of treatment effectiveness and safety within each database**

1. PS-matched cohorts: Within each surveillance cohort by frailty status (frail vs non-frail), we will use logistic regression that estimates the probability of receiving the drug of interest as a function of sociodemographic characteristics, diseases, prescription drugs, comorbidity index, and frailty index. Note that PS model will be fit separately by frailty status. We will perform a 1:1 ratio nearest-neighbor PS matching, with a caliper of 0.2 of the standard deviation of the logit PS (9). We will evaluate balance in covariates using standard mean difference (<0.1 is considered adequate balance) within each surveillance cohort.
2. Primary analysis for effectiveness and safety: For time-to-event analysis of the effectiveness and safety endpoints, we will use Cox proportional hazards regression to estimate the hazard ratios (HR) and 95% confidence intervals (CI) by frailty status (frail vs non-frail). The follow-up will begin on day 1 and end on the day of development of the effectiveness or safety endpoints or the earliest of the following censoring events: switching or discontinuation of the study drug, death not due to the outcome of interest, disenrollment, and end of data period (see Figure 2). Proportional hazards assumptions will be checked using Schoenfeld residuals.
3. Subgroup analyses for primary effectiveness and safety endpoints will be conducted by frailty status (frail vs non-frail):
  - a. age (65-74 years vs  $\geq 75$  years)
  - b. sex
  - c. race (black or non-black)
  - d. dual eligibility for Medicaid
  - e. major multimorbidity burden/pattern (informed by latent class analysis)
  - f. dementia (CCW definition)
  - g. HF hospitalization status ( $\geq 2$  or  $< 2$  in the past year)

4. Secondary analyses will be conducted by frailty status (frail vs non-frail):
  - a. secondary endpoints (individual components of primary effectiveness and safety composite endpoints)
5. Sensitivity analysis for primary effectiveness and safety endpoints will be conducted by frailty status (frail vs non-frail):
  - a. “intention-to-treat” analysis with a maximum follow-up time of 1 and 2 years from the index date
  - b. exposure risk window or grace period of 14 days
6. Adjustment for multiple testing in detecting signal: We will use the maximum sequential probability ratio testing (maxSPRT) procedure to keep the overall type-1 error rate of 0.05.  
(10)

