## STUDY POPULATION

1. Study population (see Figure 2) is created for each calendar interval.
2. Initiation of ARNI or comparator (ARB)
  - a. ARB: any of azilsartan, candesartan, eprosartan, Irbesartan, losartan, Olmesartan, telmisartan, valsartan
  - b. Index date (day 0): prescription fill from July 7, 2015

3. Assessment of eligibility (eligibility assessment window: [-365, 0] days) – See Appendix for list of codes.
  - a. Continuous enrollment for medical and drug insurance (Part A, B, and D)
  - b. Diagnosis of HF (outpatient diagnosis x2 or inpatient x1)
  - c. Reduced EF (<45%) algorithm (5)
  - d. No prior use of ARNI or comparator (exposure wash-out window: [-365, -1] days)
  - e. No recent HF hospitalization, defined as HF diagnosis (Appendix) in the primary position in the inpatient dataset (outcome wash-out window: [-60, 0] days)
  - f. No recent nursing facility stay, defined as any of the following claims in [-60, 0] days
    - i. Place of service: 31 (skilled nursing facility), 32 (nursing facility), 33 (custodial care facility)
    - ii. CPT codes: 99301, 99302, 99303, 99311, 99312, 99313, 99315, 99316, 99379, 99380, G0066
  - g. Excluded if age <65 years or exposure to both drugs on day 0
  - h. Contraindication to either drug (exclusion assessment window: [-60, 0] days, unless specified otherwise)
    - i. Hypotension
    - ii. Chronic kidney disease stage IV or V or dialysis
    - iii. Acute kidney injury
    - iv. Hyperkalemia
    - v. Angioedema: [-beginning of data, 0] days
  - i. If a patient meets the above-mentioned eligibility criteria more than once, only the first record will be included.

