## 2. Outcomes

- a. Effectiveness endpoint:
  - i. Primary: a composite of all-cause death or HF hospitalization
    - Note cardiovascular death was not used because National Death Index data were only available up to 2016. Instead, all-cause death was used.
    - HF hospitalization is defined as HF diagnosis primary position in the inpatient dataset
  - ii. Secondary: individual components separately
- b. Safety endpoint:
  - i. Primary: a composite of SAE, defined as any hospitalization or ED visit due to diagnosis codes in the primary position:
    - hypotension
    - acute kidney injury/acute kidney failure
    - hyperkalemia
    - angioedema
  - ii. Secondary: individual components

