## 3. Covariates

- a. Sociodemographic information: age, sex, race, dual eligibility
- b. Diseases: Chronic Conditions Data Warehouse (CCW) chronic conditions (see Table 2), provided in the Medicare Beneficiary Summary File (first date of satisfying the claims-based algorithm for individual conditions is available; considered present if this date is earlier than the index date)
- c. Prescription drugs: ATC3 classes with prevalence threshold  $>1\%$  in a representative Medicare sample
- d. Gagne combined comorbidity score (6)
- e. Claims-based frailty index (7): Frailty status will be defined as non-frail if  $<0.20$  or frail if  $\geq 0.20$

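### The propensity score and its balance check leave out prior-year HF hospitalization, the history of a primary-endpoint component that the plan already needs for a subgroup

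*Protocol*

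**What the plan says.** Under Statistical Analysis, item 1, the protocol fits a logistic PS model within each surveillance cohort and frailty stratum "as a function of sociodemographic characteristics, diseases, prescription drugs, comorbidity index, and frailty index". The Covariates section spells these groups out:

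- Demographics: "Sociodemographic information: age, sex, race, dual eligibility".
- Diseases: the conditions in Table 2, headed "CCW Chronic Conditions". Each is coded by its first qualifying date and "considered present if this date is earlier than the index date".
- Drugs: ATC3 classes above a 1% prevalence threshold.
- A combined comorbidity score and a claims-based frailty index.

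After 1:1 matching, the protocol states: "We will evaluate balance in covariates using standard mean difference", with values below 0.1 taken as adequate. The Cox analysis in item 2 names no further adjustment.

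Three other places bear on the point:

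- The primary effectiveness endpoint (Measurements, Outcomes) is "a composite of all-cause death or HF hospitalization".
- Study Population item 3.e excludes patients with a recent HF hospitalization, but only within the "outcome wash-out window: [-60, 0] days".
- Subgroup item 3.g stratifies by "HF hospitalization status", at two or more versus fewer than two in the past year.

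**The concern.** How often a patient was recently admitted for HF is the direct history of one component of the primary endpoint. It may also influence whether a clinician starts ARNI or an ARB. The protocol treats it as important enough to define a subgroup, but neither matches on it nor lists it for the balance check.

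If the arms still differ in this history after matching, the hazard ratio for death or HF hospitalization carries residual confounding, in either direction. The balance criterion could be met in full and still say nothing about it. Pooling the three databases would not remove a bias that they share; it would only narrow the interval around it. The maxSPRT procedure controls error from repeated testing, not confounding. A persistent bias could therefore trigger or mask a reportable signal.

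**Working it through.** **Text check**

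| Place in protocol | Does it carry prior HF hospitalization? |
|---|---|
| Demographics | No |
| Conditions in Table 2 | No; coded present or absent by first date, so no count or recency of admissions |
| ATC3 drug classes | Not directly |
| Comorbidity score, frailty index | Not stated; defined by citation only |
| Balance check | Applies to covariates, and the Covariates section does not list it |
| Cox model | No added adjustment named |
| Eligibility 3.e | Removes days -60 to 0 only |
| Subgroup 3.g | Needs the past-year count, split at 2 |

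Admissions in days -365 to -61 are therefore not restricted, matched on or balance-checked.

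**Scale of possible bias**

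The protocol gives no figure to reproduce, so every prevalence and risk ratio (RR) here is assumed. For a binary factor with post-match prevalence p1 in the ARNI arm and p0 in the ARB arm, and with RR conditional on the matched covariates, the effect estimate is multiplied by approximately

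B = [1 + p1(RR − 1)] / [1 + p0(RR − 1)].

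For example, with p1 = 0.30, p0 = 0.20 and RR = 2: B = 1.30/1.20 = 1.083.

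| History | p1 vs p0 | RR 1.5 | RR 2 | RR 3 |
|---|---|---|---|---|
| Any admission | 30% vs 20% | 1.045 | 1.083 | 1.143 |
| Any admission | 20% vs 30% | 0.957 | 0.923 | 0.875 |
| Two or more | 10% vs 5% | 1.024 | 1.048 | 1.091 |
| Two or more | 5% vs 10% | 0.976 | 0.955 | 0.917 |

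**Against the plan's own balance limit**

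For 30% vs 20%, the standardized mean difference (SMD) is 0.10 / √[(0.30×0.70 + 0.20×0.80)/2] = 0.10 / √0.185 = 0.232, over twice the limit of 0.1.

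If the variable were held to |SMD| < 0.1 with p0 = 20%, solving for p1 gives about 16.2% to 24.1%. Across that range, B lies within 0.983 to 1.019 at RR 1.5, 0.968 to 1.035 at RR 2, and 0.945 to 1.059 at RR 3.

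**For orientation**

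The background trial quoted in the protocol had risks of 21.8% vs 26.5%, a ratio of 0.82 (different comparator and endpoint). On the log scale, ln(1.083)/|ln(0.823)| = 0.080/0.195, or about 41% of that effect. For B = 1.045 the share is about 23%, and for B = 1.143 about 68%.

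**The case against.** The plan does not contradict itself here. A subgroup variable examines effect modification and need not be a PS term. A separate analysis plan could also extend the covariate list. This does not remove the point, because the protocol spells out the PS covariate groups and, on that specification, the variable is absent.

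Much indirect control already exists. Patients must meet the reduced-EF algorithm. Those with an HF admission or nursing-facility stay in the last 60 days are excluded, as are those with recent hypotension, acute kidney injury, hyperkalemia or advanced kidney disease. Matching is done within frailty strata on drug classes, a comorbidity score and a frailty index. All this will shrink any imbalance, but how much of the admission history these items carry cannot be judged from the protocol.

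The absence of heart failure from Table 2 carries little weight. Every patient has HF, so that row would be nearly constant and would hold no admission history.

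Running subgroup 3.g will produce counts by arm at the two-or-more split, so an analyst could notice an imbalance there. That is fair, but the counts are not part of the prespecified balance check. The split also merges patients with none and one admission, so it cannot show the any-versus-none difference used in the main example. Nor does the subgroup analysis change the primary estimate.

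Finally, the size is wholly assumed. At RR 1.5 the bias is about 2% to 5% either way, and the SMD limit itself would still allow about 2%. This stands, and it limits how strongly the point can be put.

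**Conclusion.** The point holds. As specified, the PS model and the SMD check omit HF hospitalization in days -365 to -61, although subgroup 3.g requires the past-year count and the primary endpoint includes the same event.

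Whether this biases the hazard ratio, by how much and in which direction cannot be determined from the protocol. On the assumed inputs (residual differences of 5 to 10 percentage points, RR 1.5 to 3), the multiplier runs from about 1.02 to 1.14, or 0.98 to 0.88 if reversed. The low end is small; the high end is material for a comparative effectiveness estimate. The defect does not depend on that size, because the planned balance check does not cover the variable. It should be corrected, with medium confidence in its practical impact.

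**What to change.** Define the number of HF hospitalizations in days -365 to -61 before the index date, in categories 0, 1 and 2 or more, using the endpoint definition (HF diagnosis in primary position, inpatient dataset). Then:

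1. Add it to the Covariates section and to the PS model in Statistical Analysis item 1.
2. Add it to the SMD table for every frailty stratum, surveillance cohort and database.
3. Where early cohorts are sparse, collapse it to 0 versus 1 or more.

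The cost is small. The data are needed for subgroup 3.g anyway, although 3.g fixes only the split at two, so the three-level count and its definition must be written down. The covariate enters about 66 PS models: 11 half-year cohorts from July 2015 to December 2020, × 2 frailty strata × 3 databases. There may be slightly fewer matched pairs. At the very least, the balance-table row alone would cost almost nothing and would show whether an imbalance exists.

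### History of hypotension, acute kidney injury and hyperkalemia in days -365 to -61 is neither excluded, directly matched on nor balance-checked, so the primary safety hazard ratio is open to residual confounding that the plan would not show

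*Protocol*

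**What the plan says.** Four places in the protocol bear on this.

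- **Matching model** (Statistical Analysis, item 1). The probability of receiving the drug is modelled "as a function of sociodemographic characteristics, diseases, prescription drugs, comorbidity index, and frailty index", separately by frailty status, followed by 1:1 matching.
- **Covariate definitions** (Measurements, 3. Covariates). The disease term is "Diseases: Chronic Conditions Data Warehouse (CCW) chronic conditions (see Table 2), provided in the Medicare Beneficiary Summary File". Table 2 lists "Chronic Kidney Disease" and hypertension, but not hypotension, acute kidney injury or hyperkalemia. The remaining terms are sociodemographic variables, ATC3 drug classes, a combined comorbidity score and a claims-based frailty index.
- **Exclusions** (Study Population, item 3.h). The heading is "Contraindication to either drug (exclusion assessment window: [-60, 0] days, unless specified otherwise". Hypotension, acute kidney injury and hyperkalemia fall under this default window. Angioedema alone is excluded back to the start of the data.
- **Primary safety endpoint** (Measurements, 2. Outcomes). It is "a composite of SAE, defined as any hospitalization or ED visit due to diagnosis codes in the primary position", and the codes are those for hypotension, acute kidney injury or failure, hyperkalemia and angioedema.

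The balance criterion is: "We will evaluate balance in covariates using standard mean difference (<0.1 is considered adequate balance) within each surveillance cohort". The Cox model in Statistical Analysis, item 2, has no stated covariate adjustment beyond the matching.

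**The concern.** An earlier episode of an outcome plausibly predicts the next one. If it also differs in frequency between the two groups of starters, it confounds the comparison. Here the history of three of the four safety components can be measured in the same claims, over a look-back the protocol already requires, yet it is absent from the stated covariate set.

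Matching is the only stated control for confounding. The planned diagnostic covers covariates, and these histories are not among them, so a clean balance table would say nothing about them. The sequential test in item 6 controls the type-1 error rate, not bias. Item 8 ties reporting to a significant pooled signal on a primary endpoint. A hazard ratio shifted in either direction could therefore delay a safety signal or create one.

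**Working it through.** The protocol gives no figure on this point, so there is nothing to reproduce. The check has two parts.

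**1. What is covered.** The exclusion covers days -60 to 0. The remaining look-back runs from day -365 to day -61, which is 365 - 61 + 1 = 305 days. As a share of the 365 days before index, 305/365 = 0.836, about 84%.

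| Safety component | Excluded, days -60 to 0 | Excluded before day -60 | Named covariate | In balance check |
|---|---|---|---|---|
| Hypotension | yes | no | no | no |
| Acute kidney injury | yes | no | no | no |
| Hyperkalemia | yes | no | no | no |
| Angioedema | yes | yes, all available data | no | not needed |

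**2. How much it could matter.** For a binary history with prevalence p1 in the matched ARNI arm and p0 in the matched ARB arm, and risk ratio RR for the safety endpoint (taken as equal in both arms), the hazard ratio is multiplied by approximately

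B = (1 + p1(RR - 1)) / (1 + p0(RR - 1)).

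The standardized mean difference that the balance check would show, if it were run on this variable, is

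SMD = (p1 - p0) / sqrt((p1(1 - p1) + p0(1 - p0)) / 2).

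The values of p1, p0 and RR are assumptions. The protocol gives none of them.

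| p1 (ARNI) | p0 (ARB) | SMD | B at RR 2 | B at RR 4 |
|---|---|---|---|---|
| 5% | 5% | 0.00 | 1.00 | 1.00 |
| 5% | 7% | -0.08 | 1.05/1.07 = 0.98 | 1.15/1.21 = 0.95 |
| 5% | 10% | -0.19 | 1.05/1.10 = 0.95 | 1.15/1.30 = 0.88 |
| 10% | 20% | -0.28 | 1.10/1.20 = 0.92 | 1.30/1.60 = 0.81 |
| 15% | 10% | +0.15 | 1.15/1.10 = 1.05 | 1.45/1.30 = 1.12 |

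B is also what a true hazard ratio of 1.00 would read. The 5% vs 7% row would pass the 0.1 threshold, so adding these histories to the check would still allow a bias of 2 to 5%. The 5% vs 10%, 10% vs 20% and 15% vs 10% rows would fail the threshold, but the planned check does not look at these variables.

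**The case against.** A reader might infer more: that the safety hazard ratio is confounded because clinicians steer patients with such a history away from ARNI, and that ARNI will therefore look safer than it is. The protocol does not support that.

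- **Differential prescribing is not shown.** Item 3.h lists these conditions as contraindications to either drug. A contraindication shared by both drugs pushes patients away from both, whereas confounding needs a difference between them. No prevalence by arm is given.
- **The direction is not known.** The only comparative safety figures, in Background item 2, are for ARNI against enalapril: hypotension 14.0% vs 9.2%, renal failure 3.3% vs 4.5%, hyperkalemia 16.1% vs 17.3%. The first might make a prescriber cautious with ARNI, but the other two point the other way. None of them is against an ARB, and none uses this protocol's endpoint of hospital or emergency visits with a primary-position code. They cannot be used to size the bias.
- **Proxies exist.** Chronic kidney disease, diabetes, hypertension, drug classes, the comorbidity score and the frailty index are all in the model, within frailty strata. What matters is the imbalance left after matching on these, and it may be small. The components of the two scores are not in the document, so how much they capture cannot be judged from it.
- **The exclusion list is wide.** In the Appendix, the codes headed chronic kidney disease stage IV or V or dialysis also include stages 1 to 3 and unspecified disease. Applied as written, they would remove further patients with recorded kidney disease.

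All of this stands against the stronger claim. None of it closes the gap. The wide kidney list also acts only in the last 60 days. A summary score or a related diagnosis does not guarantee balance on a specific history, and nothing planned would show whether balance was reached. Nor is this a detail simply left to an analysis plan, because the protocol itself states the covariate set.

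**Conclusion.** The point holds as a gap in control and in diagnostics, not as a demonstrated bias. For three of the four primary safety components, history in days -365 to -61 is neither excluded, directly matched on nor checked for balance. The safety hazard ratio is therefore open to residual confounding that the planned check would not reveal.

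Size and direction are unknown. Across the assumed post-matching prevalences and a risk ratio of 2 to 4, the bias factor runs from 0.81 (10% vs 20%) through 1.00 (equal prevalence) to 1.12 (15% vs 10%). With a small residual gap of 5% vs 7% it is 0.95 to 0.98. These ranges rest wholly on assumed inputs and on a simple formula for one binary confounder with the same effect in both arms. The change is worth making because it is cheap and bears on a primary endpoint.

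**What to change.** Using the Appendix code lists and the existing 365-day look-back, define three indicators over days -365 to -61: any hypotension, any acute kidney injury, any hyperkalemia. Add all three to the propensity model and to the table of standardized mean differences in every surveillance cohort. Angioedema needs none, since it is excluded over all available data.

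Report history of a primary-position inpatient or emergency claim for each of the three conditions in the balance table only. Enter it in the propensity model where counts allow, because rare flags can make small models unstable.

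No new data are needed. The cost is three covariates per model, over up to 11 half-year cohorts (July 2015 to December 2020) x 2 frailty strata x 3 databases = 66 models, and possibly slightly fewer matches in small early cohorts. If the histories prove balanced, the table will show it; if not, the model can correct for them.

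### Balance is set to be checked only at surveillance-cohort level, so imbalance inside the seven item 3 subgroups can go unseen; the past-year HF-hospitalization count is not a named PS covariate

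*Protocol*

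**What the plan says.** STATISTICAL ANALYSIS, item 1 describes one matching procedure. The model is placed at a stated level: "Within each surveillance cohort by frailty status (frail vs non-frail), we will use logistic regression". The same item adds: "Note that PS model will be fit separately by frailty status". Its inputs are covariate groups, entered "as a function of sociodemographic characteristics, diseases, prescription drugs, comorbidity index, and frailty index". Matching is 1:1 nearest neighbour, "with a caliper of 0.2 of the standard deviation of the logit PS". One balance rule follows: "We will evaluate balance in covariates using standard mean difference (<0.1 is considered adequate balance) within each surveillance cohort".

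Item 3 opens with "Subgroup analyses for primary effectiveness and safety endpoints will be conducted by frailty status" and lists age, sex, race, dual eligibility, multimorbidity pattern, dementia and number of past-year HF hospitalizations. It does not say which matched sample is used, whether the Cox model is adjusted, or whether balance is examined inside the subgroup levels.

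MEASUREMENTS, item 3 (Covariates) names age, sex, race and dual eligibility. Dementia enters through the CCW conditions in Table 2. The past-year HF-hospitalization count is not listed. Nor is the latent class, and its input variables are not given.

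**The concern.** The protocol already refits the PS for one effect modifier, frailty, but describes no counterpart for the seven factors in item 3. Its only numeric safeguard is an SMD taken over the surveillance cohort. Imbalances of opposite sign in two subgroup levels largely cancel in that figure, so it can pass while each level fails the protocol's own limit.

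The study aims to learn how ARNI compares with ARB across different kinds of older patients. A subgroup contrast invites the reading that the drug works in one group and not in another. If part of the contrast is residual confounding, the stated diagnostic gives no warning.

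**Working it through.** The protocol gives no subgroup size, confounder strength or interaction strength, so there is no figure to reproduce. All inputs below except the matching method, caliper and SMD limit are assumptions.

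**1. Can the cohort-level check miss subgroup imbalance?** Take two equal subgroup levels and a binary confounder with prevalence p1 in ARNI and p0 in ARB users, reversed in the other level. The true HR is 1.

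- SMD = (p1 − p0) / √{[p1(1 − p1) + p0(1 − p0)] / 2}
- Confounded rate ratio = (p1·h + 1 − p1) / (p0·h + 1 − p0), with h the confounder's HR

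For 0.55 against 0.45: SMD = 0.10 / √0.2475 = 0.20 in one level and −0.20 in the other. Over the cohort both arms have prevalence 0.50, so the SMD is 0. With h = 2 the rate ratio is 1.55 / 1.45 = 1.07 in one level and 0.94 in the other. For 0.525/0.475 the SMDs are ±0.10 and the ratios 1.03/0.97. For 0.60/0.40 they are ±0.41 and 1.14/0.88. Exact cancellation is built into this example.

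**2. Does the stated matching produce it?** Simulation: main-effects logistic PS, 1:1 nearest neighbour, caliper 0.2 SD of the logit PS, 12 replicates of 8,000 patients, and a subgroup of 15 to 30%. One prognostic covariate has log-odds for ARNI of 0.5 per SD outside the subgroup. The HR column is the approximation exp(0.3 × SMD), for log HR 0.3 per SD and a true HR of 1.00.

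| Log-odds inside subgroup | Whole-cohort absolute SMD | SMD inside subgroup | exp(0.3 × SMD) |
|---|---|---|---|
| 0.5 (equal) | near 0 | near 0 | about 1.00 |
| 0.3 | at most 0.01 | −0.13 to −0.19 | 0.96 to 0.95 |
| 0.2 | at most 0.01 | −0.22 to −0.24 | 0.94 to 0.93 |
| 0.0 | at most 0.01 | −0.34 to −0.44 | 0.90 to 0.88 |

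A separate run gave whole-cohort SMD of at most 0.001 and subgroup SMD of −0.10 (0.3 against 0.5) to −0.30 (0.0 against 0.5). Across both runs the range is exp(0.3 × −0.10) = 0.97 to exp(0.3 × −0.44) = 0.88, that is, 3 to 12%.

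**3. Harsher cross-check with a fitted Cox model.** Here 12 runs of 12,000 patients used a binary confounder with HR 2 whose log-odds for ARNI is +g in one half of the cohort and −g in the other, a reversal of direction.

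- g = 0: subgroup SMDs 0.005/−0.005, HRs 0.995/0.987, with only about 61% of pairs agreeing on the subgroup factor.
- g = 0.5: whole-cohort SMD 0.016 (passes), subgroup SMDs 0.245/−0.270, HRs 1.09/0.91.
- g = 1.0: whole-cohort SMD 0.022 (passes), subgroup SMDs 0.474/−0.536, HRs 1.18/0.84.

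**4. Factor outside the PS.** A subgroup factor left out of the PS, correlated 0.4 with a PS covariate and affecting drug choice (log-odds 0.5 to 1.0), gave SMDs inside its levels of up to about 0.10 in absolute value with no interaction at all. The whole-cohort SMD was 0.003.

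**5. What repairs it.** With the interaction in the PS (setting of step 3, g = 0.5 and 1.0), mean subgroup HRs were 0.988 to 1.018. In the extreme case of the separate run in step 2, a true HR of 1.00 read 0.885 unadjusted and 0.97 after covariate adjustment. The ratio 0.885 / 0.97 = 0.912 agrees with exp(0.3 × −0.30) = 0.914, so the remaining distance from 1.00 looks like simulation noise.

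**The case against.** Item 3 is silent. It does not say that the frailty-stratum pairs are kept, and a SAP that is not shown may add re-matching, adjustment or subgroup balance tables. Nor does item 1 exclude interaction terms from the PS. This stands: re-use of the matched sample is the natural reading of a protocol with one matching step, but it is an inference. What silence does not answer is that the one balance rule the protocol does fix sits at a level that cannot show imbalance inside the item 3 subgroups.

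A reader might infer that splitting matched pairs is itself the fault. The results contradict that. At g = 0 about 39% of pairs were discordant on the subgroup factor, yet balance and HRs were sound. The problem is a PS that omits an interaction or a factor, and nothing in the protocol shows that drug choice really does differ across these subgroups.

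The assumed coefficients also deserve caution. The 12% end needs a covariate's influence on prescribing to vanish inside the subgroup, and step 3 needs it to reverse. A latent class built entirely from listed conditions would be a function of PS covariates, which weakens the case for 3e; the case for 3g does not depend on that.

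Finally, compulsory re-matching inside every subgroup would fit large PS models to small cells, and pooling intervals to avoid this would depart from the 6-month cohorts. That objection is accepted and shapes the fix.

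**Conclusion.** The point holds in a limited form. The protocol's stated balance check cannot vouch for the seven subgroup comparisons, and one subgroup factor, the past-year HF-hospitalization count, is absent from the named PS covariates. Under the assumptions shown, subgroup HRs could be off by about 3 to 12% while the cohort-level SMD passes. With equal coefficients and the factor in the PS, the imbalance essentially disappears.

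Two stronger readings are not supported. The protocol does not show that the subgroup HRs will be confounded, since it gives neither interaction nor confounder strengths. Nor would the check normally read exactly zero: the simulations gave up to about 0.02, which still passes. The mechanism leaves the primary frailty-stratum analysis untouched, and signal reporting in item 8 depends on the pooled primary endpoints, not on subgroups. A change is worth making because it is cheap and subgroup contrasts are easily over-read.

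**What to change.** - MEASUREMENTS, item 3: add the past-year HF-hospitalization count to the PS covariates, and state which variables form the latent class. The addition also changes the PS used for the primary analysis, so it should be made once, for both.
- STATISTICAL ANALYSIS, item 3: state which matched sample each subgroup analysis uses, and evaluate SMDs within each subgroup level by frailty stratum on that sample.
- In the same item, pre-specify that subgroup Cox models adjust for the PS and for key covariates whose within-subgroup SMD exceeds 0.1. Name the key covariates in advance. The trigger uses baseline data only, not outcomes.
- Re-estimating the PS and re-matching within subgroup levels can be a sensitivity analysis where numbers allow.

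The cost is extra programming and a somewhat longer balance report. No new data are needed.
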